## 2.3. Exploratory Objective(s)

### 2.3.1. Exploratory Efficacy Objectives

- To evaluate LAR on days 8, 29, 57, and 85
- To evaluate whether a single prophylactic SC administration of REGN1908-1909 inhibits a wheal-and-flare response to a skin prick test with serial allergen titration with cat allergen in patients with cat allergen-triggered asthma and AR with or without conjunctivitis on days 29 and 85
- To evaluate the prophylactic efficacy of REGN1908-1909 in cat-allergic patients not living with a cat to reduce respiratory symptoms induced by a Controlled Cat Allergen Challenge on days 8, 29, 57, and 85 as measured by chest symptom questions
- To assess the prophylactic effect of REGN1908-1909 on biochemical measures of asthma control (FeNO) in patients with cat allergen-triggered asthma induced by a Controlled Cat Allergen Challenge on days 30 and 86 and measured 24 hours after challenge
- To assess the prophylactic effect of REGN1908-1909 on TNSS, TOSS, and chest symptoms up to 24 hours after leaving the EEU
- To assess the prophylactic effect of REGN1908-1909 on objective measures of nasal congestion (PNIF) in patients with cat allergen-triggered asthma induced by a Cat Allergen Challenge on 8, 29, 57, and 85
- To assess the relationship between baseline cat allergen-specific IgE levels (cat hair sIgE, Fel d 1 sIgE), total IgE, and the ratio of cat allergen-specific IgE/total IgE (cat hair sIgE/total IgE and Fel d 1-specific IgE/total IgE levels) and efficacy of REGN1908-1909
- To assess the relationship between cat allergen-specific IgE levels (Fel d 2, Fel d 4, Fel d 7, and other common allergens) at screening and baseline to evaluate the relationship between response to REGN1908-1909 and poly/mono-sensitization
- To assess the extent of REGN1908-1909 interference with the measurement of endogenous anti-Fel d1 IgE in baseline samples and its relationship to clinical benefit
- To assess the degree to which REGN1908-1909 prevents induction of type 2 inflammation in the nasal mucosa as assessed by RNA sequencing of nasal brushing on day 29.

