## **3. HYPOTHESIS AND RATIONALE**

### **3.1. Hypothesis**

A single SC dose of REGN1908-1909 600 mg (anti-Fel d 1) will reduce cat allergen-induced bronchoconstriction, as measured by an increase in time to EAR upon Cat Allergen Challenge in an EEU, in cat-allergic asthmatic patients not living with a cat compared to placebo-treated patients.

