At time point days 8, 29, 57, and 85 after randomization, patients will be exposed to the EEU for a maximum of 4 hours or until they reach EAR (FEV1 reduction $\geq 20\%$) and then monitored outside of the EEU for 6 hours for safety follow-up, and surveillance of a LAR. Although the amount of cat allergen that is nebulized into the EEU is continuously 40 ng/m³ Fel d 1 (approximately), the individual exposure increases over time in association with minute ventilation (the volume of air that can be inhaled or exhaled for 1 minute). Therefore, minute ventilation will be measured in each patient at baseline using spirometry, so that the cat allergen airborne exposure, as a product of the individual's minute ventilation and time, can be assessed at each Cat Allergen Challenge on days 8, 29, 57, and 85. Minute ventilation will be measured 1 time at baseline while the patient is at rest rather than in real time in the EEU during cat allergen exposure to minimize variability in the measurement.

Figure 1: Study Flow Diagram Schema 1

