4.4. Rescue Medication/or Prohibited Medication During Study

The use of the following concomitant medications is not permitted during the study:

1. Use of these concomitant medications within the following time period preceding any screening visit or any EEU visit:

(NOTE: Patients may be rescheduled 1 time for the screening visit or EEU visit after the time period for taking these concomitant medications has passed.)

- a. Topical or systemic first generation H1 antihistamines (5 days)
- b. Topical or systemic second generation H1 blockers (7 days)
- c. Systemic anti-H2 (8 days)
- d. Atemizole (6 weeks)
- e. Cromoglycates, leukotriene modifiers (7 days)
- f. Systemic steroid treatment (8 weeks prior to screening and during the study)

(NOTE: systemic steroid treatment is allowed if clinically indicated for a LAR treatment after exposure to cat allergen in the EEU.)

- g. Topical steroids (48 hours)
- h. Short-acting β 2 agonists (8 hours)
- i. Long-acting β 2 agonists (eg, salmeterol) (36 hours)
- j. Ultra-long-acting β 2 agonists (eg, indacaterol, vilanterol, olodaterol) (48 hours)
- k. Anticholinergics eg, Ipratropium (Atrovent 40 μ g) (12 hours)
- l. Long-acting anti-muscarinic agents (7 days)
- m. Methylxanthynes (eg, oral theophylline) (24 hours)
- n. Intramuscular corticosteroids (3 months prior to screening and during the study)
- o. Systemic or topical calcineurin inhibitors (14 days prior to screening and during the study)
- p. Tricyclic antidepressants/antipsychotics (14 days)
- q. Topical decongestants (72 hours)

- r. Caffeine-containing drinks or products (8 hours of EEU visits only)
2. History of systemic immunotherapy (SIT) with cat allergen or vaccines against cat allergy within 5 years of screening
3. SIT with any allergen within 6 months of screening
4. Beta-blockers during the study period
5. Immunomodulatory therapy, anti-IgE, or other biological, agent-based antagonist therapy (eg, cyclosporine) is not allowed in the 6 months prior to baseline or during the study
6. Change in prescription medications within 4 weeks before screening
7. Aspirin and any nonsteroidal anti-inflammatory drug

NOTE: paracetamol is allowed to be used for occasional pain relief.

8. Active treatment for respiratory infections (antiviral, antifungals, or antibiotics) within 4 weeks prior to screening or EEU

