4.5.3. Exploratory Efficacy Variables

The exploratory efficacy variables are:

- Time to Late Asthmatic Response (LAR) on days 8, 29, 57, and 85
- Time to Any Asthmatic Response on days 8, 29, 57, and 85
- Change and percent change from FeNO (parts per billion) (adjusted for the pre-challenge baseline) from baseline to days 30 and 86
- Change and percent change in the skin prick test with serial allergen titration, measured by AUC of the wheal sizes (diameter) over log-transformed allergen concentrations with cat allergen from baseline to day 29, 85, and 113

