The time to LAR for each treatment will be examined using Kaplan Meier estimates with patients being censored at 24 hours if they did not experience an LAR. The median time to LAR for each treatment group and the corresponding 95% confidence intervals will be presented for each Controlled Cat Allergen Challenge. A formal comparison of time to LAR in the treatment groups at each EEU challenge visit will be performed using a Cox proportional hazards model, adjusting for allergen concentration in the EEU. The Kaplan Meier and Cox Proportional Hazards models will be fit separately on the subgroup of patients who receive rescue medications upon EEU exit and for patients who do not. In patients who receive EEU related medications (including medications given on-site and rescue medications taken at-home), the impact of the carryover of medications between challenges will be explored by including taking medication or not as baseline variable for the model of each subsequent visits. A one-sided statistical test of the hazard ratio for placebo compared to drug will be performed.

The ratio of Fel d 1 IgE to Cat Allergen IgE at baseline will also be explored as potential covariate in the Cox Proportional Hazards model and will be log transformed if necessary.

If the Cox proportional hazards model does not converge, an extended Wilcoxon Rank Sum test comparing the ranks of time to LAR, adjusted by the covariates specified above, will be used ([LaVange and Koch, 2006](#)).

A time-to-event analysis with competing risks may also be used to examine the incidence of LAR, where the use of rescue medications upon EEU exit is treated as a competing risk with allergen concentration as a covariate in the model. The comparison of LAR-specific and rescue medication-specific cumulative incidences within 24 hours of an EEU challenge across treatment groups will be performed using Gray's method. The model will be fit for each EEU Challenge visit.

As an additional sensitivity analysis, the presence or absence of an LAR within the 24-hour period in the REGN1908-1909 treatment group as compared to placebo will be tested using a Fisher's Exact Test.

The time course of asthma response comprising both EAR and LAR will also be visualized and summarized. A similar analysis will be repeated for the time to any Asthma Reaction. The first asthma reaction that occurs, whether it occurs while the patient is in the EEU, in the on-site 6-

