hour observation period, or in the at-home monitoring period, will be treated as the event time. If the subject experiences no asthmatic reaction at a given Allergen Challenge visit, the patient's time will be censored at 24 hours. Kaplan-Meier estimates and curves will be produced for each visit.

The presence or absence of any asthma exacerbation (EAR or LAR) in the REGN1908-1909 treatment group as compared to placebo will be tested using a Fisher's Exact Test.

Individual spaghetti plots and mean plots of the percent change in FEV1 over time will also be examined. LOCF will be used in the calculation for any graphical displays of the mean change in FEV1 over the Cat Allergen Challenge.

The peak TNSS and TOSS and change from pre-challenge baseline to peak TNSS and TOSS across EEU challenge visits may also be examined using MMRM models.

The change and percent change from the Baseline Cat Allergen Challenge in the Fractional exhaled Nitric Oxide (FeNO) (adjusted for the pre-challenge baseline) will be explored using an MMRM model, with the treatment, visit, and treatment by visit interaction, and use of steroid rescue medications within 24 hours of the EEU challenge as factors. The time in EEU will be included as a covariate in the model.

The skin prick test with serial allergen titration with cat allergen will also be compared between treatment groups using an MMRM model, with the treatment, visit and treatment by visit interaction as factors.

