8. Titrated SPT with Serial Allergen Titration with cat allergen will be performed at screening visit 3, days 29, 85, and 113. On days when an allergen challenge is performed, the test will be performed prior to allergen challenge.
9. FeNO is assessed during screening, Visit 4 and then 24 hours after EEU exposure at day 30 and day 86.
10. All safety assessments performed at screening have to be normal and checked against the inclusion/exclusion criteria prior to REGN1908-1909 administration on day 1 (baseline).
11. On day 1, vital signs are taken prior to PK draw, prior to REGN1908-1909 administration, and at 2 hours (± 10 min) after completion of the injection.
12. Vital signs are taken prior to entry into the EEU, at exit from the EEU, and prior to leaving the clinical trial unit, and any additional times as needed.
13. Telephone call to collect AEs and concomitant medications, including any medications used from the rescue treatment kit, up to 24 hours after the EEU exposure.
14. Total blood draw at any visit will never exceed 60 mL. Blood volumes are never to exceed 350 mL in 12 weeks.
15. Samples are collected prior to administration of REGN1908-1909.
16. On day 1, urine pregnancy test is completed prior to administration of REGN1908-1909 in women of childbearing potential. Postmenopausal women do not need urine pregnancy testing.
17. Total IgE and allergen-specific serum IgE levels (Fel d 2, Fel d 4, Fel d 7).
18. Genomic analysis is mandatory for all patients enrolling in the study. One DNA sample is to be collected on day 1/randomization, but if this sample collection was omitted at baseline, it can be collected at any subsequent visit. [REDACTED]
19. PK samples are drawn at any time in the outpatient visit day from day 8 through day 113 (end of study) visit.
20. After exiting the EEU, patients are monitored outside the EEU in an observation room for approximately 6 hours.

21. Patients will be observed for 6 hours in the observation room after receiving a single dose of REGN1908-1909 or placebo.
22. Blood draws should be performed before the EEU exposure
23. Cat EEU visit 3 and visit 6 must be spaced at least 3 weeks apart
24. Assessments and procedures at the unscheduled visit(s) are to be performed at the discretion of the principle investigator.
25. Screening visits 1 and 2 may be combined into 1 visit if the patient has a historical, positive cat SPT or cat IgE that was completed in the last 12 months.

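### The only planned FeNO model adjusts for time in the EEU and steroid rescue, both arising after randomisation, so no model estimates the randomised effect on FeNO

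*SAP*

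**What the plan says.** The FeNO objective in Protocol 2.3.1 opens "To assess the prophylactic effect of REGN1908-1909 on biochemical measures of asthma control (FeNO" and places the measurement 24 hours after challenge, on days 30 and 86. SAP 4.5.3 defines the variable as change and percent change, "adjusted for the pre-challenge baseline) from baseline to days 30 and 86". SAP 5.6.3 then gives one analysis, an MMRM with treatment, visit, treatment-by-visit and "use of steroid rescue medications within 24 hours of the EEU challenge as factors. The time in EEU will be included as a covariate".

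Other sections show where the two added terms come from:

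- **Time in the EEU.** After randomisation, "patients will be exposed to the EEU for a maximum of 4 hours or until they reach EAR" (SAP 1.1). The trial hypothesis is a benefit "as measured by an increase in time to EAR upon Cat Allergen Challenge in an EEU" (Protocol 3.1).
- **Steroid rescue.** SAP 4.4 notes that "systemic steroid treatment is allowed if clinically indicated for a LAR treatment after exposure to cat allergen in the EEU". The late response (LAR) is itself an exploratory endpoint.

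No FeNO model without these terms appears in SAP 5.6.3, in the summary table of SAP 10.1 or in Protocol section 10. The opening of SAP section 5 sets general descriptive statistics for continuous variables.

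On timing, footnote 9 of the schedule says "FeNO is assessed during screening, Visit 4 and then 24 hours after EEU exposure at day 30 and day 86". The table also marks Visit 2, the saline challenge. No FeNO is scheduled just before the day 29 or day 85 challenge.

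Two neighbouring analyses in SAP 5.6.3 are relevant. The titrated skin prick test (SPT) MMRM lists treatment, visit and their interaction but no baseline wheal AUC. For LAR, the formal comparison is a Cox model adjusted for allergen concentration, followed by: "The Kaplan Meier and Cox Proportional Hazards models will be fit separately on the subgroup of patients who receive rescue medications upon EEU exit" and, likewise, on those who do not.

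**The concern.** A treatment coefficient estimates the randomised effect only if the other terms in the model are not consequences of treatment, or if they neither affect the outcome nor share a cause with it. Here both added terms follow the challenge, and time in the EEU is essentially time to EAR. Holding it fixed can distort the contrast in two ways.

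- **Exposure pathway.** If a longer stay raises FeNO, fixing the stay removes a real consequence of the drug. The contrast then looks more favourable than the total effect.
- **Shared cause.** If airway reactivity both shortens the stay and raises FeNO, a patient on drug who leaves at a given time tends to be more reactive than a placebo patient who leaves at that time. The contrast then looks less favourable.

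The two pull in opposite directions, so a reader could not tell whether the single planned contrast overstates or understates the drug's effect on FeNO.

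**Working it through.** **Check on the planning inputs.** The documents give no power, SD or effect size for FeNO, so there is no FeNO figure to reproduce. The EEU stay can be modelled from SAP 2.2: medians 58 and 132 minutes, hazard ratio 0.44, one-sided 5%, 8 of 60 lost (26 per arm), censoring at 240 minutes. With exponential times, the event probabilities are 1 − 0.5^(240/58) = 0.943 and 1 − 0.5^(240/132) = 0.716. Expected events are 26 × (0.9432 + 0.7164) = 43.15. Power = Φ(√(43.15/4) × |ln 0.44| − 1.645) = Φ(1.05), about 85% against the stated 84%, so this model of the stay is consistent with the plan.

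**Separation in stay.** Mean stay = (m/ln 2)(1 − 0.5^(240/m)).

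- m = 58: 78.9 min
- m = 132: 136.4 min, 57.5 min (0.96 h) longer than placebo
- m = 80 (assumed, a weaker effect): 101.0 min, 22.1 min (0.37 h) longer

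**Simulation, all FeNO inputs assumed.** There were 26 patients per arm and 4,000 trials per cell, with one visit fitted by least squares as a stand-in for the MMRM. Exit time is exponential, scaled by exp(−b·u) for an unmeasured reactivity trait u, rounded up to 10 minutes and limited to 10–240. FeNO change = −δ·drug + r·u + g·hours + noise, with SD about 1. LAR occurs only after EAR, at 50% (the validation study in Protocol section 1), and half of LARs receive steroid. The entries are the planned-model contrast minus the contrast without the two terms, in SD; plus is against the drug. Medians are 58 and 132 minutes.

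| Exposure effect g | (b,r) = (0,0) | (0.3,0.3) | (0.6,0.5) | (0.9,0.7) |
|---|---|---|---|---|
| 0 | 0.00 | +0.05 | +0.14 | +0.21 |
| 0.1 SD/h | −0.09 | −0.04 | +0.05 | +0.14 |
| 0.2 SD/h | −0.19 | −0.13 | −0.03 | +0.06 |

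The first column is close to −g × 0.96, the exposure pathway alone. The first row is the shared cause alone. With medians 58 and 80 the whole range is −0.08 to +0.08.

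**Power for a 0.5 SD direct benefit, one-sided 5%, without the terms / planned model (%), same column order.**

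- g = 0: 56/49, 55/43, 56/35, 56/28
- g = 0.1: 43/50, 43/44, 44/34, 47/28
- g = 0.2: 28/50, 31/44, 33/34, 38/27

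**A second simulation with a different structure.** It used 1,000,000 patients per scenario, pre-challenge FeNO in both models, and steroid use of about 22% on placebo and 12% on drug. The two contrasts agreed when neither pathway existed (−0.50 and −0.50). Otherwise they differed by 0.04 to 0.27 residual SD, in either direction. The 0.27 came from a scenario with outcome SD 1.55, so it is 0.27/1.55 = 0.17 outcome SD.

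**Steroid term.** Over 72 scenarios (3,000 trials each; steroid given in 25%, 50% or 100% of LARs; steroid effect 0 or −0.5 SD), adding the steroid factor to the time term moved the contrast by only −0.03 to +0.01 SD. Time in the EEU drives the distortion.

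**SPT.** With equal variances and correlation ρ between baseline and follow-up, the variance with the baseline covariate relative to a change score is (1 − ρ²)/(2(1 − ρ)) = (1 + ρ)/2. For assumed ρ of 0.3 to 0.7 this is 0.65 to 0.85.

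**The case against.** The strongest reply is that comparing FeNO at equal exposure is a sensible question. The baseline challenge lasts at most 2 hours and later ones up to 4. Protocol 10.4.3.2 adjusts the AUC for different exit times, and SAP 5.6.2 has an exposure-adjusted sensitivity analysis. Where longer exposure raises FeNO, the planned model can also have more power (50% against 28% in one cell). This stands as a reason to keep the model. It does not make it an estimate of the randomised effect: it targets a different quantity, needs an assumption of no unmeasured common causes, and the SAP states neither.

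Four further points reduce the concern.

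- **Steroid rescue.** None of the 20 cat-allergic patients in the validation study needed escalation beyond a short-acting β2 agonist (Protocol section 1). The steroid term matters in principle but should not carry equal weight.
- **Visit.** The 58 and 132 minute medians are day-8 assumptions, and FeNO is never measured after the day-8 challenge. With half-lives of about 30 and 21 days (Protocol 3.2.3), day 85 is 84/30 = 2.8 and 84/21 = 4 half-lives after dosing. The smaller separation may be more relevant.
- **Descriptive statistics.** Arm means under the general rule would give an unadjusted look at FeNO, but not a planned model-based contrast.
- **Meaning of the time term.** If it meant the baseline challenge it would precede randomisation. Where SAP 5.6.2 wants a baseline-challenge time it says so, so the current visit is the natural reading.

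A reader might infer that the LAR comparison shares the defect. It does not: the all-patient Cox model is already the formal comparison and has no rescue term, and an all-patient Fisher test is also planned.

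**Conclusion.** The point holds for FeNO. One model is planned, it conditions on two variables that on the natural reading follow randomisation, and no model-based estimate of the total randomised effect is listed. Time in the EEU is the main concern.

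Under assumed inputs the departure is roughly −0.2 to +0.2 SD if the day-8 separation held at the FeNO visits, and about −0.08 to +0.08 SD with a smaller one. These figures rest on an assumed FeNO SD, exposure effect, reactivity trait and steroid use.

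A reader might infer a known bias for or against the drug. The documents do not support that, because the sign depends on which pathway dominates. Nor do they support the inference that the time term is simply a mistake, or that nothing about FeNO will be reported by arm. FeNO, SPT and LAR are exploratory, and the primary day-8 analysis is unaffected. The SPT item concerns precision only, since change from baseline is already unbiased under randomisation. The LAR item is optional wording.

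**What to change.** - **FeNO.** In SAP 5.6.3 add, as the analysis of the randomised effect, an MMRM of FeNO change with treatment, visit, treatment-by-visit, the Visit 4 value (after the baseline challenge, the value being subtracted) and the Visit 2 value (pre-challenge) as covariates. Leave out time in the EEU and steroid rescue. Naming the two values also settles which measurement the baseline adjustment uses. Keep the current model as a labelled supplementary analysis, state that it compares FeNO at equal exposure, and say which challenge the time term refers to.
- **SPT.** Add baseline (Visit 3) wheal AUC as a covariate, as SAP 5.6.2 does for FEV1 AUC.
- **LAR (optional).** Add a sentence saying that the fits split by rescue at EEU exit are descriptive.

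The cost is one extra FeNO fit, one degree of freedom in the SPT model and some SAP wording, with no new data. The total-effect contrast includes any FeNO rise from longer stays on drug (about +0.10 to +0.19 SD at an assumed 0.1 to 0.2 SD per hour under the day-8 separation). It can therefore have less power than the current model, for example 31% against 44%. That rise is part of the total effect and is the reason to retain the current model beside it.

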5.6.4. Adjustment for Multiple Comparison

There is no adjustment for multiplicity for the primary or secondary efficacy variables.

5.7. Analysis of Safety Data

The analysis of safety and tolerance will be performed on the SAF, as defined in Section 3.3.

The safety analysis will be based on the reported AEs and other safety information (clinical laboratory evaluations, vital signs and 12-lead ECG).

Thresholds for Potential Clinically Significant Values (PCSV) in laboratory variables, vital signs and ECG are defined in Section 10.3.

The summary of safety results will be presented for each treatment group.

5.7.1. Adverse Events

The verbatim text, the PT, and the primary SOC will be listed in subject listings. Summaries that include frequencies and proportions of patients reporting AEs will include the PTs and the SOCs.

AEs will also be summarized by relationship to EEU procedure. Also, asthma related AEs, specifically, reported throughout the study will be presented for each treatment group and will be summarized by relationship to EEU procedure. Medications used to treat any asthma related AEs will also be listed and summarized by treatment group.

Period of observation: The observation period will be divided into two segments: pre-treatment and treatment periods. The pre-treatment period is defined as the time between when the subjects

give informed consent to before the single dose of study drug. The on-treatment period is defined as the time after the single dose of study drug until the end of study (week 16).

Day 1 is the first day of investigational product, Day -1 is the day before, and there is no Day 0.

Pre-treatment AEs are defined as AEs that developed or worsened during the pre-treatment period.

Treatment-emergent AEs (TEAEs) are defined as AEs that developed or worsened during the treatment period.

The focus of adverse event reporting in the clinical study report will be on TEAEs.

For details on handling missing data and partial dates, see Section [6](#).

Summaries of all TEAEs in each treatment group will include:

- All TEAEs by system organ class
- Possibly related TEAEs by system organ class
- Possibly related TEAEs by intensity and SOC (recommended)
- Time to first occurrence of any (or selected) TEAE (optional)
- Alert terms: all and possibly related TEAEs (optional)
- Serious adverse events: All and possibly related TEAEs by seriousness criterion
- Serious adverse events: All and possibly related TEAEs by SOC
- Death: All and possibly related TEAEs by SOC
- Other significant adverse events: All and possibly related TEAEs by “other significant” adverse event criterion
- Discontinuation: All and possibly related TEAEs by system organ class
- Non-serious possibly related TEAEs by SOC (mandatory if study includes a German center)

Counts will be provided according to treatment group for each PT within each SOC. Percentages will be calculated using the number of patients from the safety population in each treatment group.

Primary SOCs will be sorted according to the order described in the Guideline on summary of product characteristics (December 1999, European commission), with the total overall classes coming first and labeled “Any class”. Within each primary SOC, PTs will be sorted by decreasing frequency of investigational product.

A second type of table with counts of each primary SOC in decreasing order of frequency will be provided. A third type of table with counts of each PT in decreasing order of frequency will also be provided.

Common TEAEs (preferred terms $\geq 1\%$ in any treatment group) and very common TEAEs (preferred terms $\geq 5\%$ in any treatment group) will be summarized in the report.

The description of very common TEAEs will also be performed for demographic factors including: gender, age (<65, >=65), and race.

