**9.5.2. Evaluation of Causality****Relationship of Adverse Events to Study Drug:**

The relationship of AEs to study drug will be assessed by the blinded investigator and will be a clinical decision based on all available information. The following question will be addressed:

Is there a reasonable possibility that the AE may have been caused by the study drug?

The possible answers are:

**Not Related:** There is no reasonable possibility that the event may have been caused by the study drug

**Related:** There is a reasonable possibility that the event may have been caused by the study drug

The investigator should justify the causality assessment of each SAE.

A list of factors to consider when assessing the relationship of AEs to study drug is provided below. Please note that this list is not exhaustive.

Is there a reasonable possibility that the event may have been caused by the study drug?

No:

- due to external causes such as environmental factors or other treatment(s) being administered
- due to the patient's disease state or clinical condition
- do not follow a reasonable, temporal sequence following the time of administration of the dose of study drug
- do not reappear or worsen when dosing with study drug is resumed
- are not a suspected response to the study drug based upon preclinical data or prior clinical data

Yes:

- could not be explained by environmental factors or other treatment(s) being administered
- could not be explained by the patient's disease state or clinical condition
- follow a reasonable, temporal sequence following the time of administration of the dose of study drug
- resolve or improve after discontinuation of study drug
- reappear or worsen when dosing with study drug
- are known or suspected to be a response to the study drug based upon preclinical data or prior clinical data

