##### Analysis

All AEs reported in this study will be coded using the currently available version of the Medical Dictionary for Regulatory Activities (MedDRA®). Coding will be to lowest-level terms. The verbatim text, the preferred term (PT), and the primary system organ class (SOC) will be listed.

Summaries of all TEAEs by treatment group will include:

- The number (n) and percentage (%) of patients with at least 1 TEAE by SOC and PT
- TEAEs by severity (according to the grading scale outlined in Section 9.5.1), presented by SOC and PT
- TEAEs by relationship to treatment (related, not related), presented by SOC and PT

Deaths and other SAEs will be listed and summarized by treatment group.

Treatment-emergent adverse events leading to permanent treatment discontinuation will be listed and summarized by treatment group.

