10. APPENDIX

10.1. Summary of Statistical Analyses

Efficacy Analysis:

Endpoint	Analysis Populations	Primary Analysis	Statistical Method	Supportive Analysis	Subgroup Analysis	Other Analyses
Primary Endpoint						
Time to EAR	FAS, PPS	Time to EAR (a 20 % drop in FEV1 or when the subject exits the EEU on day 8 due to clinically significant symptoms), censored at 4 hours if the patient does not experience an EAR	Cox proportional hazards model	Yes Kaplan Meier estimates and plots	No	Sensitivity Analysis: Fisher's exact test comparing the proportion of subjects with EAR
Secondary Endpoints						
Time to EAR	FAS, PPS	Time to EAR (a 20 % drop in FEV1 or when the subject exits the EEU on days 29, 57, and 85 due to clinically significant symptoms), censored at 4 hours if the patient does not experience an EAR	Cox proportional hazards model	Yes Kaplan Meier estimates and plots	No	Sensitivity Analysis: Fisher's exact test comparing the proportion of subjects with EAR
AUC of FEV1	FAS	Percent change in the AUC of FEV1 from baseline to days 8, 29, 57, and 85	MMRM	No	No	No
AUC of TNSS	FAS	Change in the AUC of TNSS from baseline to days 8, 29, 57, and 85	MMRM	No	Yes	No

Endpoint	Analysis Populations	Primary Analysis	Statistical Method	Supportive Analysis	Subgroup Analysis	Other Analyses
AUC of TOSS	FAS	Change in the AUC of TOSS from baseline to days 8, 29, 57, and 85	MMRM	No	Yes	No
Cat allergen quantity	FAS	Change and percent change in cat allergen quantity as experienced by patients from baseline to days 8, 29, 57 and 85	MMRM	No	No	No

Safety Analyses:

Endpoint	Analysis Populations	Primary Analysis	Statistical Method	Supportive Analysis	Subgroup Analysis	Other Analyses
Adverse Events	FAS	Percent of patients by system organ class	Descriptive Statistics	No	No	No

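### SAP 5.7.1 specifies a severity table only for possibly related TEAEs, although protocol 10.4.4.1 requires severity for all TEAEs

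*SAP*

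**What the plan says.** **Protocol 10.4.4.1 (Analysis).** The list opens with "Summaries of all TEAEs by treatment group will include". Two of its items are "TEAEs by severity (according to the grading scale outlined in Section 9.5.1), presented by SOC and PT" and, separately, "TEAEs by relationship to treatment (related, not related), presented by SOC and PT". Severity and relationship to treatment are therefore two different summaries, and neither restricts the other.

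**SAP 5.7.1.** The corresponding list starts with "All TEAEs by system organ class". Its only item that mentions intensity is "Possibly related TEAEs by intensity and SOC (recommended". The same section adds that "asthma related AEs, specifically, reported throughout the study will be presented for each treatment group and will be summarized by relationship to EEU procedure".

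**SAP Appendix 10.1.** The row for adverse events gives the analysis as "Percent of patients by system organ class".

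**The concern.** The protocol promises a randomized comparison of severity across all TEAEs. The SAP specifies that comparison only for events an investigator has already judged possibly related to study drug, and its tag makes even this table a recommendation.

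The restriction has particular force in this trial. Patients with asthma undergo repeated allergen challenges, and protocol 9.5.2 names, among the considerations that point away from the drug, an event being "due to external causes such as environmental factors or other treatment(s) being administered" and the patient's own disease state. A reported asthma or allergic event can reasonably be coded as not related to study drug on either ground. It would then fall outside the only severity table that the SAP specifies. Safety and tolerability is a stated secondary objective and TEAE incidence a secondary endpoint, so the severity profile by arm is part of what the study is meant to describe. Filtering it on a causality opinion gives up an unconditional comparison that randomization supports.

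**Working it through.** No sample size, power or error rate enters, so the check is a comparison of texts.

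1. **Protocol scope.** The parent line in 10.4.4.1 covers all TEAEs by treatment group. Severity by SOC and PT is one item beneath it and has no causality condition.

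2. **SAP 5.7.1, item by item.**
   - All TEAEs by SOC: 1 item, no severity.
   - Possibly related TEAEs by SOC: 1 item, no severity.
   - Possibly related TEAEs by intensity and SOC: 1 item, with severity, related events only.
   - Time to first occurrence and alert terms: 2 items, both marked optional, no severity.
   - Serious events by criterion, serious events by SOC, deaths, other significant events, discontinuations: 5 items, each covering all and possibly related TEAEs, no severity.
   - Non-serious possibly related TEAEs by SOC: 1 item, no severity.

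   Total: 1 + 1 + 1 + 2 + 5 + 1 = 11 summaries. One carries severity. None carries it for all TEAEs or for those judged not related.

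3. **Rest of the SAP.** The remainder of 5.7.1 adds SOC and PT frequency tables, common TEAEs, and very common TEAEs by demographic factor, all without severity. The asthma-related summary is split by relationship to the EEU procedure. Appendix 10.1 gives SOC percentages. SAP 6.3 says how to class a TEAE of missing intensity in intensity tables, which presupposes such tables but specifies none.

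4. **Which events are affected.** Protocol 9.5.2 allows two answers on relationship to study drug, related or not related; I take the SAP's possibly related to mean related. Any reported TEAE answered not related leaves the severity table. Protocol 9.4.1 and SAP 4.6.1 set the boundary: asthmatic and allergic symptoms expected in response to the EEU are outcome measures, so they enter no adverse event table under either document. What remains includes EEU events outside expected symptoms, events qualifying as serious, asthma or allergic events not in response to a challenge, and unrelated TEAEs of any other kind.

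5. **Where those events still appear.** They are counted in the all-TEAE tables, in the serious-event tables if serious, and in the asthma-related summary if asthma-related, without a severity grade.

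6. **Data available.** Protocol 9.5.1 and SAP 4.6.1 grade severity for every adverse event, whatever its causality. Nothing new has to be collected.

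**The case against.** The strongest reply is that little is lost. Serious TEAEs are tabulated whether related or not, and protocol 9.3.2 names intensive treatment for allergic bronchospasm as an example of an important medical event, so the gravest asthma events reach a comparative table. Asthma-related events and the medications used to treat them are presented by arm. Rescue medication use, time to early and late asthmatic response, and the Fisher test of any asthma exacerbation compare the arms without any causality filter. This stands. A reader might infer that an imbalance in severe asthma events would be invisible in the planned output, and the documents do not support that. What is missing is the mild, moderate and severe breakdown of reported TEAEs judged not related. Serious-event tables do not supply it, because seriousness (protocol 9.3.2) and severity (protocol 9.5.1) are separate classifications.

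A second reply is that the SAP list is not exclusive: it says what the summaries will include, and the rule in SAP 6.3 speaks of TEAE intensity tables without limiting them to related events. The tags for recommended and optional items, and one table tied to German centers in a single-site French study, look like template text left unedited. This also stands, in that a reader should not conclude that the sponsor decided to drop the table. An all-TEAE severity table is not forbidden. But a summary the protocol requires should be specified in the SAP.

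Two further inferences should be resisted. Protocol 9.5.2 does not instruct investigators to answer not related for allergen-driven or asthma events; it gives a non-exhaustive list of factors for a clinical judgment, and SAP 6.3 classes a missing relationship as related. And the silence of SAP 1.2.3 proves nothing, because that list records changes between SAP versions, not departures from the protocol.

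**Conclusion.** The concern holds as a mismatch between protocol and SAP in safety reporting. The protocol requires severity for all TEAEs; the SAP specifies it only for possibly related TEAEs, as a recommended item, and restores the wider table nowhere else. The consequence is that the severity of reported, not-related TEAEs would not be compared between arms, although the events themselves would be counted.

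The documents contain no adverse event counts, so the number of events affected cannot be stated. No efficacy test, analysis population or data collection is touched, and expected EEU-induced symptoms lie outside the issue. The conclusion assumes that the tables produced would follow the SAP list as written, and that possibly related corresponds to the protocol's related category. It is worth correcting because it restores a protocol commitment at very little cost.

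**What to change.** In SAP 5.7.1, add as a required output all TEAEs by severity, SOC and PT, by treatment group on the safety analysis set, and repeat it in Appendix 10.1. Name the protocol 9.5.1 scale as the grading basis, since SAP 4.6.1 refers injection site reactions to a different scale. Keep the related-only intensity table as a supplement and replace its tag with a definite status. Optionally, add severity to the asthma-related adverse event summary. If the sponsor does intend the narrower table, the SAP should record and justify the departure from the protocol.

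The cost is SAP wording and one more output, two with the optional addition. This is a reporting change only and alters no clinical management rule.
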